#### **Start Date Imputation Rules**

- **Missing start day, but month and year present:**
  - If the event occurs in the same month and year as Baseline, then the start day of the event will be assigned to the day Baseline (i.e., Day 1).
  - Otherwise, the start day will be set to the first day of the month.
- **Missing start day and month, but year present:**
  - If event occurs the same year as Baseline, then the start date of the event will be assigned to Day 1.
  - Otherwise, the start day and month will be set to 01 January.

- **In the unlikely event of a completely missing start date, the start date will be imputed as Day 1.**
- **If the year and day are present, but month is missing, apply imputation rules as though the day is also missing, and only year is present.**
- **If the imputed start date is after the non-imputed end date, then the start date will be set to the end date.**

### **End Date Imputation Rules**

- **Missing end day, but month and year present:**
  - The day will be set to the last day of the month.
- **Missing end day and month, but year present:**
  - The end day and month will be set to the date of study completion.
  - However, if study completion year is greater than the year of the event, then the day and month will be set to 31 December.
- **Missing all components of an end date and the event is not marked as ongoing:**
  - The event will be considered as ‘ongoing’ and will be considered study-emergent for AEs and concomitant for medications if the start date is on or after Day 1.
- **If the year and day are present, but month is missing, apply imputation rules as though the day is also missing, and only year is present.**
- **If the imputed end date is before the start date, then the start date will be set as the end date.**
- **If the imputed date is later than the date of study withdrawal, then the date of study withdrawal will be imputed for the date.**

In subject data listings, start and end date of events will be displayed as reported on the CRF (i.e., imputed values will not be listed).

#### **4.1.11.3 Imputation for Alphanumeric Data**

Should there be instances where a clinical laboratory parameter is reported with imbedded non-numeric characters, as for example, “<0.1” or “>10”, the data will be imputed for quantitative summaries. The actual values as reported in the database will be presented in data listings.

For incorporation in quantitative summaries, the following imputation rules will be employed:

- The lower limit of quantification will be replaced with  $\frac{1}{2}$  the value of the lower limit. For example,  $< 0.1$  will be replaced with 0.05.
- The upper limit of quantitation will be increased by one level of precision that precedes the value. For example, “ $>0.1$ ” will be imputed to “0.11”, and “ $>10$ ” will be imputed to “10.1”.

#### 4.1.12 Handling of outliers

Outliers will be identified to ensure the validity and robustness of the statistical analyses. The following methods may be used to detect outliers in the dataset:

- **Data visualization:** Boxplots, scatterplots and histograms may be used to visually identify points that appear to deviate from the overall distribution.
- **Statistical criteria:** For select continuous variables, values falling more than  $+/- 3$  standard deviations above or below the mean will be flagged as potential outliers. For select categorical variables, frequencies containing  $<3\%$  of the overall data will be reviewed to identify any unusual, improbable, or implausible categories.
- **Clinical context:** Outlying data points will also be assessed in the context of clinical plausibility and data collection procedures to determine whether outliers are likely data errors or true anomalies. For example, 2-Minute Walk Test (2MWT) distances exceeding 300 meters will be excluded from analyses as these values are implausible for this study patient population (Bohannon, 2017).

Once identified, outliers may be handled by any or a combination of the following procedures:

- **Verification:** Data flagged as outliers may be cross-checked against EDC, eCRF and source records to rule out data entry errors and confirm true anomalies.
- **Documentation:** Outliers will be documented as likely data entry errors, likely valid but extreme observations, or data with an unknown cause.

For outliers that are deemed to be valid but extreme observations:

- Sensitivity analysis may be conducted with and without outliers to assess their impact on results
- Outliers will be included in the primary analysis but may be interpreted jointly with sensitivity analysis if their influence impacts the resulting conclusions and yields findings that are not robust

All decision regarding handling outliers, including their identification and inclusion/exclusion from analyses, will be documented in detail in a Statistical Report and in the CSR.

#### **4.1.13 Protocol Deviations**

A protocol deviation is any noncompliance with the clinical trial protocol or International Council for Harmonization (ICH) of Technical Requirements for Pharmaceuticals for Human Use Good Clinical Practice (GCP) requirements. The noncompliance may be either on the part of the subject, the investigator, or the study site staff. Protocol deviations will be recorded on the source documents and with an explanation for the deviation. All protocol deviations will also be recorded as specified in the monitoring plan. Protocol deviations will be identified by site staff, through medical reviews, and by clinical research associates during site monitoring.

Deviations will be classified as minor or major prior to the database lock. Major protocol deviations are defined as those that result in harm to the study subjects or significantly affect the scientific value of the reported results of the study. Other deviations will be considered minor.

All protocol deviations will be summarized in a table and well as presented in a listing, including their assigned severity (major/minor). Major protocol deviations will be analyzed separately, and sensitivity analysis may be conducted to assess whether conclusions change when excluding subjects with major deviations. Subgroup analysis may be conducted to evaluate whether protocol deviations disproportionately affect specific subject groups.

Note that visits that occurred outside of visit windows may be identified as a protocol deviation, and these are expected to be relatively common in this study. Some out of window visits may have already been mapped to the appropriate closest visit in the data collection and therefore will not be excluded from the population analysis sets. Protocol deviations due to out of window visits are classified as ‘minor’ unless they occur 90 or more days out of window, in which case they are classified as ‘major.’

### **4.2 Background Characteristics**

The following sections describe outputs to be generated for subject background characteristics. In addition to the tables specified in this section, supportive listings will be produced.

#### **4.2.1 Subject Disposition and Accountability**

The number of subjects who were enrolled, completed the study, and discontinued from the study, along with the reason for discontinuation, will be summarized.

#### **4.2.2 Demographics and Baseline Characteristics**

Demographics and Baseline Characteristics will be summarized for the following Populations and Subgroups:

- Study Population
  - Prodromal
  - Symptomatic ALSP (Non-HSCT + Prior HSCT)
    - Symptomatic ALSP (Non-HSCT)
    - Symptomatic ALSP (Prior HSCT)

- Study Population (Non-HSCT)
  - Prodromal
  - Symptomatic ALSP (Non-HSCT)

The following Demographics and Baseline Characteristics will be summarized:

- Age at baseline (continuous variable), calculated as [(Date of Baseline – Date of Birth) / 365.25] and rounded down to the nearest integer
- Age at diagnosis (continuous variable)
- Duration since diagnosis in years, calculated as [(Date of Baseline - ALSP Diagnosis Date)/365.25] and rounded to 1 decimal place.
- If subject had prior HSCT, time in months from HSCT procedure to Baseline visit, rounded to 1 decimal place
- Sex (categorical variable)
- If Female, woman of child-bearing potential (WOCBP) (categorical variable)
- Height (continuous variable)
- Weight (continuous variable)
- Body Mass Index (BMI), calculated as weight/height, i.e., kg/m^2
- Country of origin (categorical variable)
- Ethnicity (categorical variable)
- Race (categorical variable; note more than race may be selected)
- Location where the subject was initially consulted (categorical variable)
- Genetically confirmed CSF1R mutation (categorical variable)
  - If genetically confirmed:
    - Exon Number frequency between 18-21 (i.e., inside the tyrosine kinase domain) versus exons 2, 4, 8, 11, 12, 13, 14, 15, 16, 17 (i.e., outside the tyrosine kinase domain)
    - Amino Acid sequence (categorical variable)
    - Nucleic Acid sequence (categorical variable)
- Cognitive Assessments
  - MoCA
  - CDR®+NACC-FTLD Global Score
  - CDR®+NACC-FTLD Sum-of-Boxes
  - CBFS Total Score
- Motor Assessments (Ambulatory Population)
  - 2MWT
  - TUG
- Severity of Illness Scales
  - CGI-S
  - PGI-S
- Other Functional and Psychiatric Assessments (Caregiver Population)
  - FAQ
  - NPI-12
  - ZBI

- Biomarkers
  - Neurofilament light chain (NfL) (Serum)
  - Glial fibrillary acidic protein (GFAP) (Serum)
  - GFAP (CSF)
  - NfL (CSF)
  - sCSF1R (CSF)
  - Soluble triggering receptor expressed on myeloid cells 2 (sTREM2) (CSF)
- MRI
  - Ventricle Volume
  - Adjusted total gray matter volume
  - Corpus callosum thickness
  - Corpus callosum volume
  - Whole brain volume
  - White matter lesion volume
  - Brain volume composite
  - ALSP MRI Severity score

#### **4.2.3 Medical History**

Medical History will be coded using the Medical Dictionary for Regulatory Activities (MedDRA) version 24.0 or higher and summarized for the Study Population. Medical History will be summarized by System Organ Class (SOC) and Preferred Term (PT).

#### **4.2.4 Family History**

The following Family History variables will be summarized for the Study Population by Subgroup:

- Have any family members been diagnosed with ALSP, have ALSP symptoms, and/or have genetic confirmation of CSF1R mutation? (categorical “Yes/No” variable)
  - If Yes:
    - Relationship with the Subject (categorical variable)
    - Family member diagnosed with ALSP? (categorical variable)
    - Age at Diagnosis (continuous variable)
    - Does the family member have a documented CSF1R mutation? (categorical variable)
      - If Yes:
        - Exon Number frequency between 18-21 (i.e., inside the tyrosine kinase domain) versus exons 2, 4, 8, 11, 12, 13, 14, 15, 16, 17 (i.e., outside the tyrosine kinase domain).
        - Amino Acid sequence (categorical variable)
        - Nucleic Acid sequence (categorical variable)
        - Mutation Type (categorical variable)
      - Symptoms observed in family member:
        - Cognitive Impairment / Dementia (categorical variable)

- Psychiatric Symptoms (categorical variable)
- Motor Impairment (categorical variable)
- Gait Disorder (categorical variable)
- Seizures (categorical variable)
- Oromotor and Speech Disturbance (categorical variable)
- Sensory and Visual Disturbance (categorical variable)
- Autonomic Symptoms (categorical variable)
- Other Findings (categorical variable)

#### **4.2.5 Prior and Concomitant Medications**

All prescription and over-the-counter medications that have been taken during the 30 days before Screening/Baseline through the last study visit will be documented. A complete history of medications taken for the treatment of ALSP will be collected.

Prior and concomitant medications will be coded using the World Health Organization (WHO) Drug Dictionary March 2021, or later, and summarized for the Study Population. Prior and concomitant medications will be summarized separately by Anatomical Therapeutic Chemical (ATC) classification and WHO Drug generic term.

#### **4.2.6 Prior and Concomitant Procedures**

Procedures will be documented and coded using MedDRA version 24.0 or higher. Prior and concomitant procedures will be described in a listing.

### **4.3 Study Endpoints and Analysis Methods**

The following sections outline the set of proposed endpoints and corresponding analyses. In addition to the tables specified in this section, supportive listings will be produced.

#### **4.3.1 Pharmacodynamic (Biomarker) Endpoints**

The following endpoints will be analyzed to determine change over time within the Study Population and if changes from baseline differ across the subgroups. CSF biomarkers are collected in only a subset of subjects from the optional CSF Biomarker sub-study. In addition to descriptive statistics, the geometric mean and geometric CV% will also be included and will be presented by Population and Subgroup for observed value, change from baseline, and percentage change from baseline, where appropriate.

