#### **4.1.4 Sample Size and Power**

The sample size of approximately 60 subjects was determined without a formal power calculation and is expected to provide sufficient information to address the study objectives in this rare disease.

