#### **4.1.5 Level of Significance**

Unless otherwise noted, all statistical tests will be two-sided with a significance level of 0.05. P-values greater than or equal to 0.001, in general, will be presented to three decimal places. P-values less than 0.001 will be presented as “<0.001”; p-values greater than 0.999 will be

presented as “>0.999”. Confidence intervals will be presented to one more decimal place than the point estimate.

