#### **4.1.7 Descriptive Statistics**

Descriptive statistics will be used to summarize data from this study.

In general, continuous data will be summarized with number of subjects (N), number of observations (n), arithmetic mean, standard deviation (SD), median, minimum, and maximum. For fluid biomarker variables, percent coefficient of variation (%CV), geometric mean, and percent geometric coefficient of variation (%gCV) will also be presented.

The minimum and maximum will be reported to the same number of decimal places as the raw data recorded in the database. The mean, median, lower quartile and upper quartile will be reported to one more decimal place, and the SD (and the standard error [SE], if applicable) will be reported to two more decimal places than the raw data recorded in the database. In general, the maximum number of decimal places reported shall be four for any summary statistic.

Categorical data will be summarized in terms of the number of subjects providing data at the relevant time point (n) and percentages. Percentages will be presented to one decimal place. Percentages will not be presented for zero counts. Percentages will be calculated using n (the number of observations with non-missing values) as the denominator. A missing category shall be included only for categorical variables where no data is available. The missing category will be omitted if there were no missing values for that variable.

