##### **4.3.1.1 Fluid Biomarker Endpoints**

Fluid Biomarker endpoints include:

- Change from Baseline to Months 6, 12, 18, 24, 30, and 36 in NfL and other exploratory marker(s) (e.g., GFAP) in blood

- Change from Baseline to Months 12, 24, and 36 in sTREM2, sCSF1R, NfL and other exploratory marker(s) (e.g., GFAP, Osteopontin) for the CSF Population

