#### **4.3.4 Repeated Measures Analysis**

Mean changes from baseline in Ventricle Volume, MoCA, and CBFS will be analyzed using restricted maximum likelihood-based mixed effects models for repeated measures (MMRM). Separate models will be generated that consider study visit as a categorical variable, and study day as a continuous variable.

In addition the analyses described below, exploratory analyses may be conducted in which additional covariates are added to the previously described MMRM analyses to understand the influence of these covariates and how imbalance in them across may have influenced results. Additionally, if meaningful outliers are identified by the descriptive analyses, the corresponding MMRM analyses may be replicated as a sensitivity analyses in which the outlier observation(s) is omitted.

MMRM analyses may also be performed with percent change from baseline as the dependent variable for the MRI and biomarker endpoints.

Specifically, the following MMRM models will be explored as the primary models of interest:

- Mean change from baseline to last follow-up in Ventricle volume
- Mean changes from baseline to last follow-up in MoCA
- Mean changes from baseline to last follow-up in CBFS

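### SAP 4.3.1 lists geometric mean and geometric CV% for signed changes in fluid biomarkers, where they are undefined if any change is zero or negative, and gives no ratio or log-scale alternative

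*SAP*

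**What the plan says.** SAP 4.1.7 sets the general rule: "For fluid biomarker variables, percent coefficient of variation (%CV), geometric mean, and percent geometric coefficient of variation (%gCV) will also be presented". This is in addition to n, arithmetic mean, SD, median, minimum and maximum, and it is not limited to observed values.

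SAP 4.3.1 applies the rule to the biomarker endpoints: "the geometric mean and geometric CV% will also be included and will be presented by Population and Subgroup for observed value, change from baseline". The end of that list reads "change from baseline, and percentage change from baseline, where appropriate", so percentage change is covered too, subject to a qualifier that is not explained.

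SAP 4.3.1.1 defines the blood endpoint as a change: "Change from Baseline to Months 6, 12, 18, 24, 30, and 36 in NfL and other exploratory marker(s) (e.g., GFAP) in blood". The CSF markers are handled in the same way. For MRI, SAP 4.3.1.2 lists arithmetic statistics only, so the geometric wording matters chiefly for the fluid markers.

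On modelling, SAP 4.3.4 commits to three outcomes: "Mean changes from baseline in Ventricle Volume, MoCA, and CBFS will be analyzed using restricted maximum likelihood-based mixed effects models". It then adds an option: "MMRM analyses may also be performed with percent change from baseline as the dependent variable for the MRI and biomarker endpoints".

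The SAP contains no log transformation, no ratio to baseline, and no rule for zero or negative changes in a geometric summary.

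**The concern.** A geometric mean is the exponential of a mean of logarithms, and the geometric CV comes from the SD of those logarithms. Neither exists for a zero or negative value. Concentrations are positive, but a change or percent change takes either sign, and in an untreated cohort some subjects will fall at some visits. The table shell therefore asks for a number that often cannot be produced, and two programmers verifying each other under SAP 4.1.3 have no common rule for what to do.

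Choosing geometric statistics implies that the fluid markers are thought to behave multiplicatively. The summary of change that suits this, the geometric mean of post/baseline, is missing. The only alternative scale offered for a biomarker model is percent change. It is asymmetric: a halving is -50%, while the doubling that reverses it is +100%. If log-ratios vary between subjects, mean percent change exceeds the geometric mean ratio minus 1. At stake are the readability of the biomarker change tables and, if the optional model is run, the within-group change estimates and their p-values.

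**Working it through.** There is no figure in the plan to reproduce: "The sample size of approximately 60 subjects was determined without a formal power calculation", and no biomarker SD or expected change is given.

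**Inputs from the SAP.** About 60 subjects (4.1.4); two-sided level 0.05 (4.1.5).

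**Assumptions, not in the documents.** D = log(post/baseline) is normal with mean log(GMR) and SD s, where GMR is the true geometric mean ratio. Subjects are independent. The ranges examined are s from 0.1 to 0.7 and GMR from 1.0 to 1.5.

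**Step 1: is the geometric mean of change defined?** The share of non-positive changes is p = Φ(−log(GMR)/s), and the chance that all n changes are positive is (1 − p)^n. For GMR 1.25 and s = 0.3, p = Φ(−0.223/0.3) = 0.228, and 0.772^10 = 0.075.

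| GMR | s | p | n = 10 | n = 30 | n = 60 |
|---|---|---|---|---|---|
| 1.0 | any | 0.500 | 0.00098 | 9.3e-10 | 8.7e-19 |
| 1.25 | 0.1 | 0.013 | 0.88 | 0.68 | 0.46 |
| 1.25 | 0.3 | 0.228 | 0.075 | 0.00042 | 1.7e-7 |
| 1.5 | 0.1 | 0.000 | 1 | 1 | 1 |
| 1.5 | 0.3 | 0.088 | 0.40 | 0.063 | 0.0039 |

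Percent change has the same sign as change, so the same table applies to it. Only a large rise with little variation makes the statistic safe.

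**Step 2: mean percent change against the geometric ratio.** E[percent change] = 100 × (GMR × exp(s²/2) − 1), while the geometric value is 100 × (GMR − 1). The excess is 100 × GMR × (exp(s²/2) − 1). For GMR 1 and s = 0.3 this is 100 × (exp(0.045) − 1) = 4.6.

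**Step 3: effect on a within-group test.** A one-sample t-test of mean percent change against zero was simulated with GMR = 1 (40,000 runs per case). It stands in for the within-group tests that SAP 4.3.4.1 reports and is not a full MMRM.

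| s | Excess, GMR 1 (points) | Excess, GMR 1.25 (points) | Rejects, n = 20 | Rejects, n = 60 | Log-ratio test, n = 60 |
|---|---|---|---|---|---|
| 0.1 | 0.5 | 0.6 | not run | not run | not run |
| 0.2 | 2.0 | 2.5 | 5.5% | 10.5% | 5.1% |
| 0.3 | 4.6 | 5.8 | 6.7% | 16.6% | 4.7% |
| 0.5 | 13.3 | 16.6 | 9.7% | 36.4% | 5.1% |

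At n = 60 almost all of the percent-change rejections are upward. At s = 0.7 the excess with GMR 1 is 27.8 points.

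**Two-subject illustration (invented values).** Suppose 20 rises to 30 and 30 falls to 24. The changes are +10 and −6, so their geometric mean is undefined. The percent changes are +50% and −20%, with mean +15.0%. The geometric result is √(1.5 × 0.8) − 1 = +9.5%.

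**The case against.** The best defence of SAP 4.3.1 is its qualifier. It can fairly be read as letting the team omit a geometric statistic that cannot be computed, so the SAP does not strictly order an impossible calculation. That stands, but the qualifier names no case and no substitute. If the statistic is omitted, no log-scale summary of change remains.

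A reader might infer more than the documents support, in four ways:

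- **That non-positive changes will be dropped, leaving only subjects who rose.** Nothing in the SAP provides for this. SAP 4.1.7 also requires n, arithmetic mean and median, and SAP 4.3 promises listings, so a blank geometric cell would still leave change summarised on all subjects with data.
- **That the plan commits to modelling fluid biomarkers as percent change.** It does not. SAP 4.3.4 makes this optional, and the committed models cover ventricle volume, MoCA and CBFS.
- **That mean percent change is simply biased.** It is a different estimand. The excess is an error only if the geometric or median ratio is the target, and the rejections in step 3 are false positives only in that sense. The median percent change, already required, would show 0% when the median ratio is 1. In subgroup differences the excess cancels if the ratios and log-ratio SDs are equal.
- **That untreated progression will be misstated for the external control.** The integrated comparison involves a Phase 2 study with its own SAP (SAP 4.1.1), which is not available here. Whether it uses mean percent change in fluid markers is unknown.

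Nor do the documents say that the fluid markers are skewed; the choice of geometric statistics only implies it.

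**Conclusion.** The point holds for the descriptive tables. Geometric mean and geometric CV% are not valid summaries of signed change or signed percent change. SAP 4.3.1 lists both, SAP 4.1.7 sets no limit, and no ratio or log-scale summary is offered instead. This follows from the definitions and needs no assumption. How often the cell cannot be filled does depend on assumptions: nearly always with no true change, usually with a 25% rise and log-ratio SD 0.3, and never in practice with a 50% rise and SD 0.1.

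The modelling part is conditional on the optional percent-change model being run. Its size depends on an SD that the documents do not give: negligible near 0.1, a few points at 0.2 to 0.3, and large only at about 0.5 and above. It bears on within-group change more than on subgroup contrasts. Overall this is a minor point of specification in an exploratory study, worth correcting because the correction is cheap.

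**What to change.** - In SAP 4.1.7 and 4.3.1, limit geometric mean and geometric CV% to observed values and post/baseline ratios.
- For each fluid biomarker, report the geometric mean ratio to baseline with a 95% CI, by visit and subgroup.
- Keep the arithmetic mean and median for change and percent change, and replace the open qualifier with this explicit list.
- In SAP 4.3.4, state that any fluid biomarker MMRM that is run uses log(post/baseline) as the dependent variable, with results back-transformed to ratios.

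The cost is one derived variable and revised table-shell wording, with no new data. There is a small downside: log-ratios can be sensitive to very low values. If the half-limit rule for values below quantification in SAP 4.1.11.3 is applied to these assays, the logs are always defined, but a few imputed values could carry weight. They should be flagged, and the result checked without them.
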